Pain Sensitivity Index (PSI; Gross, 1992a). The PSI is a 16-item self-report measure that assesses the fearful appraisal of pain and the expected physical, psychological, and social consequences of pain. Items are rated on a scale ranging from 0 (not at all) to 7 (very much) reflecting the degree to which the item applies to the respondent. Higher scores indicate higher levels of pain sensitivity. The scale has demonstrated high internal consistency in previous studies with dental patients (α = 0.92) (Klages et al., 2004). It was found to measure a construct distinct from dental phobia and health concerns (Gross, 1992a). Pain sensitivity is considered a stable characteristic that can influence the development of situational fears (Gross, 1992b). It has been related to dental anxiety and expectation of pain before dental procedures (Klages et al., 2004). The PSI will play a dual role in this study, as a secondary outcome measure and as a hypothesized moderator of the efficacy of the Internet-based dental anxiety intervention compared to the active control condition. It will be administered at baseline and the 1-month and 3-month follow-ups.

Distress Tolerance Scale (DTS; Simons & Gaher, 2005). The DTS is a 15-item self-report measure assessing one's perceived ability to experience and tolerate negative emotional states. This scale measures four dimensions of distress tolerance: subjective appraisal of distress, ability to tolerate emotional distress, absorption of attention by negative emotions, and regulation efforts to alleviate distress. Items are rated on a scale ranging from 1 (strongly agree) to 5 (strongly disagree). Total score range from 15 to 75, with higher scores reflecting higher levels of distress tolerance. This scale has high internal consistency (α = .89), appropriate convergence with other self-report ratings of affective distress and regulation, and adequate six-month test-retest reliability (r =.61). The DTS will also play a dual role in this study, as a secondary outcome measure and as a hypothesized moderator of the efficacy of the Internet-based dental anxiety intervention compared to the active control condition. It will be administered at baseline and the 1-month and 3-month follow-ups.

Fear Questionnaire Blood-Injury-Injection Subscale (FQ-BII; Marks & Mathews, 1979). The FQ-BII is a 5-item subscale of the complete FQ. It assesses the degree to which an individual avoids situations involving blood-injury-injection because of fear, including in the context of dental procedures. Items are rated on a scale ranging from 0 (would not

Page 13 of 28 Revision: May 12, 2023

avoid it) to 8 (would always avoid it). Total scores range from 0-40 with higher scores indicating greater phobic avoidance. The FQ is sensitive to treatment-induced improvements in phobic responding, demonstrates adequate psychometric properties, and is a commonly used measure for research on phobias. The FQ-BII is included here because of evidence that suggests a modest but significant overlap between dental phobia and BII fears (van Houtem et al., 2014). It will be administered at baseline and the 1-month and 3-month follow-ups.

PROMIS-Sleep Disturbance-Short Form (PROMIS-SD-S; Yu, Buysse, & Germain, 2011). The PROMIS Sleep Disturbance Short Form is an 8-item measure that is part of the National Institute of Health's Patient-Reported Outcome Measurement Information System (PROMIS) and derived from its original longer version (Buysse et al., 2010). The PROMIS-SD-S assesses sleep disturbance over the previous 7 days. All items are rated on a 5-point scale. Total raw scores range from 8-40 (which are then converted to T-scores), with higher scores indicating greater sleep disturbance. The measure has demonstrated good psychometric properties and greater precision than other commonly used measures of sleep quality (Yu, Buysse & Germain, 2011). This measure, as well as the measure described below, are included here due to evidence that dental anxiety is associated with sleep disturbance (Almoznino et al., 2015); we hope to assess the association of dental anxiety and sleep-related difficulties in the current study and track potential improvements in sleep outcomes following dental anxiety treatment. This measure and the measure described below will be administered at baseline and the 1-month and 3-month follow-ups.

PROMIS-Sleep-related Impairment-Short Form (PROMIS-SRI-S; Yu, Buysse, & Germain, 2011). The PROMIS-Sleep-related Impairment-Short Form is an 8-item measure that is also part of the PROMIS initiative and derived from its original longer version (Buysse et al., 2010). The PROMIS-SRI-S assesses daytime impairment due to sleep difficulties over the previous 7 days. All items are rated on a 5-point scale. Total raw scores range from 8-40 (which are then converted to T-scores), with higher scores indicating greater sleep-related impairment. Like the PROMIS-SD-S, this measure has demonstrated good psychometric properties and greater precision than other commonly used measures of sleep quality (Yu, Buysse & Germain, 2011).

Sheehan Disability Scale (SDS; Sheehan,1983). The SDS is a 3-item measure of functional impairment due to one's illness in 1) work, 2) social life, and 3) family/home life. Three items assessing each of these domains are rated on a 0 (no impairment) to 10 (extreme impairment) scale which are then summed and used to assess overall current levels of disability due to illness. In the current study, we modified the scale to specifically assess the current impact of participants' dental anxiety symptoms on work/school, social life/leisure activities, and family life/home responsibilities. The validity and reliability of the SDS has been previously demonstrated among individuals with panic disorder (Leon et al, 1992) and social anxiety disorder (Hambrick et al., 2004). The SDS will be utilized as a secondary outcome measure in the current study to assess the degree of functional impairment associated with dental anxiety as well as

Page 14 of 28 Revision: May 12, 2023

improvements in functional impairment following the intervention. This measure will be administered at baseline and the 1-month and 3-month follow-ups.

Clinician-Administered Interviews

Anxiety and Related Disorders Interview Schedule for DSM-5 (ADIS-5) - Adult Version (Brown & Barlow, 2014). The ADIS-5 is a semi-structured interview designed to establish reliable diagnoses of the DSM-5 anxiety, mood, somatoform, and substance use disorders. The ADIS has been utilized in former PI [name] research on anxiety disorders since it was originally created at the Center for Stress and Anxiety Disorders, University at Albany, SUNY, where he was on staff, and he has overseen the training of many doctoral students in clinical psychology in its use in the last 30 years. To minimize participant burden, this study will utilize only the dental procedure-related section of the specific phobia module of the interview. This module includes ratings of fear and avoidance of dental procedures as well as resultant interference (the latter being used to operationalize one of the inclusion criteria). For the dental phobia diagnosis, a dimensional clinical severity rating, ranging from 0 = none to 8 = very severely disturbing/disabling, will be assigned, with scores of 4 or above denoting clinical significance. All interviews will be audio-recorded. A 20% sample will be randomly selected for assessment of inter-rater agreement on the presence of dental phobia and clinical severity. Interviewers have demonstrated excellent inter-rater agreement for the principal diagnosis of specific phobia in a mixed sample of anxiety disorder patients (κ = .86; Brown et al., 2001). The ADIS-5 module will be administered at baseline and the 1-month and 3-month follow-ups.

Post-Appointment Debriefing Ratings. Two separate sets of interview questions will be administered, one after the completion of the dental anxiety intervention and the other after completion of the following dental appointment. The debriefing interview after the dental anxiety intervention will ask the patient to rate the perceived helpfulness of each component of the intervention, the degree to which any of the components were hard to understand, and the degree of difficulty they experienced watching each set of videos of dental procedures. It will also include an open-ended probe of patients' reactions to any aspect of the dental anxiety intervention. These questions will be asked for the purpose of collecting qualitative data on patients' reactions to the intervention, to determine whether there are differences between patients assisted by psychology versus dental staff, and to gather information to inform future modifications of the intervention. Questions will also be asked to determine the degree of pain and the degree of anxiety patients expect to experience in the dental treatment appointment they will have immediately following the dental anxiety intervention. Because this interview will not be administered to patients randomized to the active control condition, the ratings of expected pain and anxiety will be administered to them after they watch the control video.

Ratings after the dental appointment will assess the degree of pain and anxiety experienced during the appointment, the degree of pain and anxiety in comparison to past dental appointments, how much the dental anxiety intervention helped the patient

Page 15 of 28 Revision: May 12, 2023

to get through the dental procedure (for the full intervention and the major components), and the likelihood of scheduling a dental appointment in the future. The debriefing interview after the dental appointment will also include an open-ended probe of patients' thoughts about the impact that any aspect of the dental anxiety intervention may have had on their reactions to the dental procedure. An abbreviated version of this interview will be administered to active control patients, asking about pain and anxiety, and omitting any questions related to the dental anxiety intervention.

Pain Intensity Numeric Rating Scale (PI-NRS). The PI-NRS is a widely utilized 11-point measure that assesses physical pain intensity on a scale ranging from 0 (no pain) to 10 (worst possible pain). The PI-NRS has been used to assess pain intensity in several studies conducted in medical settings (Farrar et al., 2001, 2010; Rowbotham et al., 2004; van der Roer, 2006). Anxiety increases subjective pain experience, and therefore this scale will be used to assess the intensity of dental related pain that participants experienced during their scheduled dental appointment and expect to experience at their next dental appointment. The PI-NRS will be administered as part of the post-dental-appointment debriefing interview.

Attendance at Dental Appointments

Given that avoidance of dental appointments is strongly connected to dental anxiety, we will also assess whether the Internet-based dental anxiety intervention increases attendance at future dental appointments. We will utilize TUKSoD's automated scheduling system (axiUm, http://www.axiumdental.com/) to do so. It is acknowledged that attendance may be influenced by factors unrelated to dental anxiety, but it is a reasonable hypothesis that anxious avoidance plays a role in attendance, and individuals with dental phobia are less likely to visit a dentist at least once a year than persons without. Thus, it is of interest to determine whether attendance at appointments scheduled prospectively after the index appointment is affected by treatment, and we will monitor this for the following 12-month interval. These data will not be collected for active control patients, who will be offered the intervention to be administered before their first scheduled dental appointment after the completion of the 3-month follow-up.

Planned Analyses

We propose general statistical analyses and sample size considerations for the U01 trial. Initial analyses will be conducted to determine normality of distributions of the continuous variables, and any necessary transformations will be conducted. Primary outcomes will be the MDAS (score ranging from 5 to 25) and the rating of fear of dental procedures from the ADIS-5 (0=no fear to 8=very severe fear). All eligible patients will be randomly assigned to one of the three conditions described above. Although randomization should provide relatively comparable groups, demographic variables that differ between groups and are correlated with the primary outcomes will be used as covariates. Patients will receive a full battery assessment of outcome measures at baseline and 1 and 3 months after the day of their index dental appointment (as well as assessments on the day of their index dental appointment).

Page 16 of 28 Revision: May 12, 2023

Preliminary statistical analysis will include measures of central tendency and dispersion, as well as an examination of the bivariate relationships among the primary and secondary outcome variables (e.g., client satisfaction, blood-injury-injection phobia), potential moderators (e.g., distress tolerance and pain sensitivity), and demographic characteristics.

Differences between the groups on baseline demographic, clinical and psychological measures will be examined using χ^2 (Pearson) or Student's *t*-tests, as appropriate. Moreover, differences on the variables listed above among completers and drop-outs will also be explored. Both per protocol and intention to treat (ITT) analyses will then be conducted.

Specific Aim 1

Aim 1 will test the equivalence hypothesis (Ho: the two intervention conditions are not equivalent). MDAS and ADIS fear scores will be the primary outcomes to be compared between two intervention conditions for equivalence. The two one-sided tests (TOST) procedure of Schuirmann (1987) will be used to conduct the equivalence test. Linear mixed-effects models for repeated measures will be used to assess differences between intervention groups using the MDAS and ADIS fear rating as continuous outcome variables. Linear mixed-effects models will also investigate the treatment effect on dental anxiety or fear after accounting for other confounding factors. Similar analyses will be conducted for secondary outcome measures (pain sensitivity index, anxiety sensitivity index, sleep disturbance and sleep-related impairment scales, disability scale, distress tolerance scale, client satisfaction and blood-injury-injection phobia). Statistical significance will be set at p < 0.05. Multiple imputation (MI) will be used to handle missing follow-up data as described below.

Aim 1 will also determine whether the Internet-based intervention reduces dental anxiety/fear as determined by self-ratings or assessor ratings at one month and three months post-intervention. Initially, we will assess within-group change of anxiety or fear scores for each condition separately using paired *t*-tests. Linear mixed-effects models will be used to estimate within-group reduction of anxiety/fear at assessments one and three months after the administration of the intervention adjusting for other covariates.

Specific Aim 2

Aim 2 will assess the superiority hypothesis (Ho: there are no significant differences between the interventions and control). MDAS and ADIS-5 fear scores will be the primary outcomes to be compared. Initially, we will assess the differences between the interventions and control using two-sample *t*-tests. The main analysis will be based on linear mixed-effects models for repeated measures (using the MDAS score and ADIS-5 fear rating as continuous outcome variables) to assess differences between intervention and control groups. Linear mixed models will also investigate the treatment effect on dental anxiety or fear after accounting for other confounding factors. Similar analyses will be conducted for secondary outcome measures (e.g., client satisfaction and blood-

Page 17 of 28 Revision: May 12, 2023

injury-injection phobia). Statistical significance will be set at p < .05. MI will be used to handle missing follow-up data as described below.

Specific Aim 3

Aim 3 examines the impact of the intervention on attendance at scheduled dental appointments over the following 12-month period to determine whether the intervention affects avoidance of dental procedures. First, we will examine whether the overall attendance rate is changed from pre- to post-intervention using a one-sample Chisquare test comparing the 12-month periods immediately before and immediately after the delivery of the intervention. The two intervention groups combined will be used for this analysis. We will also use a Chi-square test to compare post-intervention attendance rates between the two intervention groups. We expect the attendance rates will be similar for the two groups. Finally, we will conduct logistic regression analyses predicting attendance/nonattendance among intervention patients who did or did not demonstrate reduction in dental anxiety at 3-month follow-up. Relevant demographic characteristics and other potential confounding variables or moderators will be included in the final logistic models.

Missing Data

MI will be used to handle missing follow-up data when conducting ITT analysis for Specific Aims 1 and 2. There will be three steps in the MI procedure: 1) The missing follow-up data will be filled in 100 times to generate 100 complete datasets; 2) The 100 datasets will be analyzed by analyses of covariance with follow up scores at 1-month or 3-month as outcomes and treatment groups as the independent variable (Tr1 vs. Tr2 for Specific Aim 1, or Tr1 + Tr2 vs. AC for Specific Aim 2), controlling for baseline scores; 3) The results from the 100 complete datasets will be combined for the MI inference (Rubin 1987). SAS PROC MI and PROC MIANALYZE will be used for multiple imputation analysis using SAS 9.4 (SAS Institute Inc., Cary, NC, USA).

Analysis of Secondary Objectives

To determine whether primary objectives 1 and 2 are reflected in measures of other related constructs such as pain sensitivity, distress tolerance, anxiety sensitivity, and anticipated and perceived pain and anxiety, the statistical methods described above will be used. The moderating role of distress tolerance and pain sensitivity as expressed in the secondary objectives will be assessed as well. We will examine whether baseline levels of distress tolerance and pain sensitivity moderate the efficacy of the dental anxiety intervention. We will examine the moderating effect of these factors on the intervention and the reduction in dental anxiety at the 1-month and 3-month follow-ups. For moderation analyses, we will include a dummy variable for randomization arm, the potential moderator variable (distress tolerance or pain sensitivity), and an interaction term between the two (i.e. dummy variable multiplied by the mean-centered moderator variable). To maintain power to detect moderation, we will explore moderators

Page 18 of 28 Revision: May 12, 2023

separately. We will also use linear-mixed effects models in which we include potential confounding variables, as well as main effects and interaction terms of interest.

d) Withdrawal of Subjects

We do not expect that there will be much in the way of withdrawal during the dental anxiety intervention itself, although it is not entirely out of the realm of possibility. We expect that the major concerns will have to do with the assessments over time, and in that case, concerns over withdrawal are really concerns over retention. However, we note a few issues below.

Reasons for Withdrawal related to the Intervention

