The human subjects activities for this clinical trial will take place at TUKSoD. Patients with dental anxiety will be recruited from the TUKSoD Faculty Practice Clinic (If it appears that we will fall short of enrollment milestones, additional patients will be recruited from among those receiving dental treatment at the Graduate Clinics of TUKSoD: Endodontology, Periodontology, and Advanced Education General Dentistry. See attached letters from the Directors of these clinics.). The administration of the online dental anxiety intervention will take place in the Center for Public Health Research (CPHR) of TUKSoD, which is the research laboratory of one of the study investigators, [name]. This is precisely the arrangement that was utilized in the conduct of the randomized controlled trial (Tellez et al., 2015) and in the R34 planning grant described above.

Beyond CITI training, all psychology personnel involved in the human subjects aspects of the current protocol will be highly trained in the relevant activities, which involve the administration of the online dental anxiety intervention, administration of interviews and questionnaires, conducting screening/assessment/follow-up phone calls, and the management of data. Psychology personnel will either (1) have been members of the research team for the previous clinical trial, for which most procedures will be quite similar and will have received training and practice with non-patient research assistants acting as patients in the specific details of the operation of the program, or (2) they will be persons of similar levels of training (postdoctoral fellows in clinical psychology, staff psychologists, or advanced clinical psychology doctoral students). Most of the treatment in service of the first objective will be administered by a postdoctoral fellow or clinical psychology doctoral student. Other research assistants who currently conduct solicitation calls for ongoing studies of dental anxiety will do so for the proposed protocol as well.

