A post-baccalaureate study coordinator with a background in psychology or a related field will perform many important tasks for the U01 project. After appropriate training, the study coordinator will conduct the bulk of the initial telephone screening interviews. He/she will also conduct diagnostic interviews at baseline and one-month and three-month follow-up assessments and track attendance at scheduled dental appointments for the 12-month period following the dental anxiety intervention. He/she will also complete reliability ratings for diagnostic interviews conducted by other study staff, providing full coverage of this activity with the graduate student. The study coordinator will also be charged with the rating of treatment fidelity/adherence of a portion of the

Page 6 of 28 Revision: May 12, 2023

interventions completed during the U01 project. The study coordinator will also conduct a range of data entry and management activities.

The dental staff for the proposed U01 will be two or more part-time dental assistants or expanded function dental assistants as defined in the State of Pennsylvania working with [name] at TUKSoD (one full-time equivalent). They will be trained in the administration of the Internet-based dental anxiety intervention by a psychologist, postdoctoral fellow, or doctoral student highly trained in CBT and the specific online intervention, and they will administer the dental anxiety intervention to those patients randomly assigned to the arm of the trial in which the intervention is delivered by dental staff. They will also assist in the payment of study subjects and other day-to-day tasks when these activities cannot be performed by the post-baccalaureate study coordinator.

7) Prior Approvals

See attached letters of support from the Directors of the Faculty Practice Clinic and the Graduate Clinics of TUKSoD.

8) Study Design

a) Recruitment Methods

Approximately 550 patients will participate in this research, roughly evenly divided between the three arms of the study.

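### Nothing in the plan masks the 1- and 3-month raters of ADIS-5 fear, a primary outcome, and the coordinator who conducts follow-up interviews has other duties that can reveal the arm

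*Combined protocol and SAP*

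**What the plan says.** Section 8(c), Planned Analyses, states: "Primary outcomes will be the MDAS (score ranging from 5 to 25) and the rating of fear of dental procedures from the ADIS-5". The second of these is a 0 to 8 score assigned in an interview (8(c), Clinician-Administered Interviews). Aims 1 and 2 both test it.

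On concealment, 8(c), Enrollment/Baseline (Time 1), has senior research staff run a computer-generated randomization from a restricted file. The coordinator is told only to book the visit, and the arm is withheld until the patient has arrived and consented in person. The plan says nothing about who may know the arm after that.

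Section 6 gives the study coordinator several duties:

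- Interviews: "He/she will also conduct diagnostic interviews at baseline and one-month and three-month follow-up assessments".
- Attendance: "track attendance at scheduled dental appointments for the 12-month period following the dental anxiety intervention". For this measure, 8(c), Attendance at Dental Appointments, adds: "These data will not be collected for active control patients".
- Fidelity: "The study coordinator will also be charged with the rating of treatment fidelity/adherence of a portion of the" interventions (the sentence runs over a page break).
- Agreement checks: "complete reliability ratings for diagnostic interviews conducted by other study staff, providing full coverage of this activity with the graduate student".

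Section 9, under Recording, adds that fidelity ratings and the coordinator's informal viewing of session videos feed back to dental assistants in training. Section 6 also describes the training of psychology personnel in activities "which involve the administration of the online dental anxiety intervention, administration of interviews and questionnaires".

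**The concern.** A score assigned by an interviewer can move with what the interviewer believes about the treatment. The plan states its expectations openly in Section 5: I-CBT should beat control, and dental and psychology delivery should do equally well. A rater who knows the arm could shift the ADIS-5 fear difference in Aim 2, and could widen or narrow it in Aim 1. Concealment before the intervention does not prevent this, because the primary ratings come one and three months later.

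**Working it through.** **Step 1: look for masking after the clinic visit.** No section says that follow-up interviewers or reliability raters are unaware of the arm, or that a person with a session role may not rate that patient. The only blinding term is in the title of a cited reference.

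**Step 2: set the possible routes side by side.**

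| Route | Where | Can reveal | How firm |
|---|---|---|---|
| Coordinator rates fidelity | Section 6 | I-CBT vs control, and who delivered | Stated duty; only some sessions; timing not given |
| Coordinator tracks attendance | Section 6; 8(c) Attendance | I-CBT vs control only | Stated duty; timing implied (step 3) |
| Coordinator views session video | Section 9, Recording | I-CBT vs control, and who delivered | Stated, but for feedback to assistants in training |
| Psychology staff deliver and interview | Section 6 | Both | No rule separates the roles for one patient; not said to occur |
| Debriefing questions in the follow-up ADIS-5 | 8(c) Follow-up Visits | Not known | Inferred; content and order not given |
| CSQ-8, for I-CBT patients only | 8(c) Other Self-Report Questionnaires | I-CBT vs control only | Inferred; nothing says the rater sees it |

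Section 9, Protection Against Risk, keeps the same assessor where possible. A rater unmasked at 1 month may therefore rate again at 3 months.

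**Step 3: timing of attendance tracking.** Section 8(b) has attendance monitoring carry on for nine months beyond the last enrollee's 3-month follow-up. The Time 5 text in 8(c) likewise says that it continues to 12 months. Both imply that tracking is already running before the 3-month rating.

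**Step 4: scale, Aim 2.** The plan gives no bias figure to reproduce, so the shifts here are assumed. From about 550 patients in three roughly equal arms, take 183 controls and 367 I-CBT patients, unadjusted, with a two-sided 5% test (two-sided is an assumption).

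- SE = sqrt(1/367 + 1/183) = 0.0905 SD.
- With no true effect and a net shift b, P(reject) = Φ(b/SE − 1.96) + Φ(−b/SE − 1.96).
- b = 0.05: b/SE = 0.553, so P = 8.0% + 0.6% = 8.6%.
- b = 0.10: b/SE = 1.105, so P = 19.6% + 0.1% = 19.7%.
- With an assumed 30% dropout, SE = 0.0905/sqrt(0.7) = 0.108, giving 7.5% and 15.2%.

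These are net shifts over a whole group. If only 20% of one group were unmasked, a net 0.10 SD would need 0.10/0.20 = 0.5 SD per unmasked patient.

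**Step 5: scale, Aim 1.** No equivalence margin is stated. With 183 per arm, SE = sqrt(2/183) = 0.1045 SD. If the true difference sits at the margin, false equivalence is 5% without a shift. A 0.10 SD shift toward zero gives about Φ(0.957 − 1.645) = 25%. The same shift away gives Φ(−0.957 − 1.645) = 0.5%. Assumed margins of 0.3 to 0.5 SD agree within 0.1 point.

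**Step 6: the planned 20% re-rating.** It covers diagnosis and clinical severity, not fear. Suppose fear were added, with an assumed ICC of 0.90, no dropout and a sample balanced by arm. The rater difference then has SD sqrt(2 × 0.10) = 0.447.

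- Aim 2 (73 vs 37): 95% half-width 1.96 × 0.447 × sqrt(1/73 + 1/37) = 0.18 SD.
- Aim 1 (37 vs 37): 1.96 × 0.447 × sqrt(2/37) = 0.20 SD.
- A 0.10 SD rater shift would be detected about 20% and 16% of the time, respectively.

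**Step 7: calendar.** August 2018 + 6 + 45 + 3 months = February 2023, before the revision date of May 12, 2023.

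**The case against.** The best defence is that access is controlled where it matters most. Senior staff randomize, the coordinator books visits without the arm, and attendance comes from an automated scheduling system that the coordinator already uses for all clinic patients, so access alone reveals nothing. Reliability ratings are of interviews done by other staff. Questionnaires at in-person follow-ups, the default, are completed in the research offices, and nothing shows the rater handling the CSQ-8. The self-rated MDAS is tested on the same contrasts, so disagreement between the two outcomes would be a visible warning.

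Much of this stands. Fidelity rating covers only some sessions, the video route is limited to assistants in training and may touch few patients, and the debriefing and CSQ-8 routes are inferences. The MDAS is a real safeguard for the trial's overall message, and discordance would be suggestive, though not conclusive.

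The attendance defence mostly fails. The act of tracking a patient marks that patient as not a control, and the timeline implies tracking before the 3-month rating.

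Two stronger readings are tempting. A reader might infer that raters will in fact know the arm and that ADIS-5 fear is biased in favour of I-CBT. The text shows only that unmasking can happen, and gives neither share nor size. A reader might also infer that the re-rating graduate student is a treating doctoral student, because Section 6 says "Most of the treatment in service of the first objective will be administered by a postdoctoral fellow or clinical psychology doctoral student". Nothing identifies the two as one person.

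**Conclusion.** The point holds as a gap in design. A primary outcome is interviewer-rated, its follow-up raters are not masked in any section, and a person who conducts follow-up interviews is assigned fidelity and attendance work that can reveal the arm. Attendance and the CSQ-8 bear only on I-CBT versus control; seeing a session also bears on Aim 1.

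The share of patients affected, the size of any bias, and its direction for Aim 1 cannot be obtained from the documents. The rise from 5% to about 20% is an illustration under an assumed net 0.10 SD shift, not an estimate. The MDAS limits the damage to the overall conclusion but leaves the ADIS-5 result unprotected. Masking may be described in a manual that was not supplied, but the protocol refers to none; if it is, one sentence in the protocol would settle the matter.

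**What to change.** 1. **Separate the roles, using existing staff.** For any patient whose follow-up ADIS-5 the coordinator rates, extract attendance and score fidelity only after the 3-month rating. No one who delivered or viewed a patient's session should rate that patient's follow-up fear. Where fidelity scores or video are needed sooner for assistants in training, use someone who does not rate that patient.
2. **Fix the order.** At each follow-up, record and lock the fear rating before any debriefing question or CSQ-8.
3. **If follow-up is already complete**, as the stated timeline suggests, items 1 and 2 are too late. Report which ADIS-5 raters held treatment, fidelity or attendance roles, and interpret ADIS-5 fear as possibly unmasked, alongside the MDAS.

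Adding the fear item to the 20% re-rating is optional. It is an agreement check only, since it would miss a 0.10 SD bias most of the time.

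The cost is later scoring, some task reassignment and a set form order, with no new visits or staff. The downside is some loss of same-assessor continuity, which Section 9 lists as a participant protection, wherever a rater must change. Deferring the fidelity and attendance work and fixing the form order avoids most of that loss.
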